4 GENERAL CONSIDERATIONS FOR ANALYSIS

4.1 Sample Size and Power Calculations

Patients may be enrolled in the study more than once in association with multiple administrations of vernakalant IV. The study targeted 2,000 patients, per administration of vernakalant IV, across participating EU countries. The target sample size was selected in order to have adequate statistical precision as expressed by a two-sided, 95% confidence limit around the expected incidence rate for each HOI for sample sizes of 500, 1,000 1,500, and 2,000 patients. The incidence of each HOI during the first 24 hours post-vernakalant IV administration among patients randomised to receive vernakalant IV in the pooled phase II/III clinical trial database (n=889, including the AVRO Study [3]) ranged from 0% to 0.22% for each HOI.

[figure not shown]
Table A shows the margins of error, defined as the distance from the expected proportion to the upper limit of the confidence interval (CI) as shown in the table, and confidence limits of the two-sided 95% confidence intervals with sample size of 500, 1,000, 1,500, and 2,000, respectively. For example, if the expected proportion of significant hypotension is 0.003 and the sample size is 1,500, the margin of error is 0.004, and the lower and upper bounds of the two-sided 95% confidence interval will be 0.001 and 0.007, respectively. The calculation of the confidence intervals was performed using the Clopper-Pearson exact method [3] and PASS software (2008, Kaysville, Utah).

Table A Margins of error and confidence limits of the two-sided 95% confidence intervals for one sample proportion with various sample sizes.

Since the confidence interval is not symmetric around the expected proportion of patients with events, the precision is the distance from the expected proportion to the upper limit of the confidence interval as shown in this table.

| Sample Size | N=500 | | N=1,000 | | N=1,500 | | N=2,000 | |
|----------------|-----------------|-----------------------|-----------------|-----------------------|-----------------|-----------------------|-----------------|-----------------------|
| Expected Prop. | Margin of Error | Lower and Upper Limit | Margin of Error | Lower and Upper Limit | Margin of Error | Lower and Upper Limit | Margin of Error | Lower and Upper Limit |
| 0.001 | 0.008 | 0.000, 0.009 | 0.005 | 0.000, 0.006 | 0.003 | 0.000, 0.004 | 0.003 | 0.000, 0.004 |
| 0.002 | 0.009 | 0.000, 0.011 | 0.005 | 0.000, 0.007 | 0.004 | 0.000, 0.006 | 0.003 | 0.001, 0.005 |
| 0.003 | 0.010 | 0.000, 0.013 | 0.006 | 0.001, 0.009 | 0.004 | 0.001, 0.007 | 0.004 | 0.001, 0.007 |
| 0.004 | 0.010 | 0.000, 0.014 | 0.006 | 0.001, 0.010 | 0.005 | 0.001, 0.009 | 0.004 | 0.002, 0.008 |
| 0.005 | 0.011 | 0.001, 0.016 | 0.007 | 0.002, 0.012 | 0.005 | 0.002, 0.010 | 0.004 | 0.002, 0.009 |
| 0.006 | 0.011 | 0.001, 0.017 | 0.007 | 0.002, 0.013 | 0.005 | 0.003, 0.011 | 0.004 | 0.003, 0.010 |
| 0.007 | 0.012 | 0.002, 0.019 | 0.007 | 0.003, 0.014 | 0.006 | 0.003, 0.013 | 0.005 | 0.004, 0.012 |
| 0.008 | 0.012 | 0.002, 0.020 | 0.008 | 0.003, 0.016 | 0.006 | 0.004, 0.014 | 0.005 | 0.005, 0.013 |
| 0.010 | 0.013 | 0.003, 0.023 | 0.008 | 0.005, 0.018 | 0.006 | 0.006, 0.016 | 0.005 | 0.006, 0.015 |
| 0.012 | 0.014 | 0.004, 0.026 | 0.009 | 0.006, 0.021 | 0.007 | 0.007, 0.019 | 0.006 | 0.008, 0.018 |
| 0.015 | 0.015 | 0.006, 0.030 | 0.010 | 0.008, 0.025 | 0.008 | 0.009, 0.023 | 0.006 | 0.010, 0.021 |

Figure A Plot of precision and margin of error at various levels of expected proportion of patients with events.

Footnote: Margin of error (half-width of confidence interval) is defined as the distance between the expected proportion (point estimate) and upper bound of the two-sided 95% confidence limit as the confidence interval is not symmetric.

4.2 Analysis Populations

All screened patients will be included in summary of patient disposition with additional summary of their demographic characteristics. All enrolled patients who meet the eligibility criteria, sign the informed consent form, and are administered vernakalant IV will be included in the analysis population set, regardless of their disposition status. If a patient's consent is withdrawn prior to completing follow-up period, all data already collected as part of the study will be retained for analysis unless country-specific ethics committee (EC) requirements prohibit this or the patient requests otherwise. In addition, patients who discontinue from the study prior to receiving vernakalant administration will not be included in the overall analysis population. All the summaries will be presented on the overall analysis population set unless otherwise stated.

Patients may be enrolled in the study more than once in association with multiple administrations of vernakalant IV. Patients with multiple enrolments are included in the analysis population, and the number of previous study enrolments is provided in the study analysis. All study analyses presented in the study tables, listings, and figures of this report treat each patient's subsequent administrations of vernakalant IV as occurring independently.

Effectiveness analysis population is defined as all patients from overall analysis population defined above EXCEPT those who receive ECV or IV Class I/III AA for cardioversion within 90 minutes of start of the first vernakalant IV administration. But for analysis of the effectiveness of

vernkalant IV, e.g., rate of conversion, both analysis population and effectiveness population may be used.

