**Vernakalant IV Sterile Concentrate Prospective Safety Registry Study**

Sponsor Protocol Identifier: 6621-049-00

3 August 2016

---

At the completion of the study, stratified analyses will be used to present the results. Full statistical methods and analyses will be described in the Statistical Analysis Plan (SAP).

Patients are consecutively enrolled into SPECTRUM based on when they present at the participating site. In order to minimize any potential selection bias at the patient level, retrospective data collection will be conducted to include all patients already treated with BrinavessTM but not enrolled in SPECTRUM, at existing and newly qualified sites, with available key data. Specifically, data will be included from all patients who;

1. Have received BrinavessTM since April 2013 but were not enrolled in SPECTRUM.
2. Have available in their hospital records the key data variables as stipulated in section 7.2.1.
3. Provide their informed consent or the site obtains a waiver from their IEC.

Both retrospectively and prospectively included patients have to fulfill the same inclusion and exclusion criteria. As neither group of patients are selected randomly, this approach is not expected to yield selection bias. In addition, results will be reported overall and stratified by method of enrollment. As those who refuse to consent to participate, will not have provided their consent to use their data it would not be possible to compare baseline characteristics of those who refuse vs those who participate. To ensure the overall sample is not dominated by any one site or country by the inclusion of retrospective data, any site or country who reaches their limit based on the inclusion of retrospective data will be closed and the resources used to open other sites/countries. Enrolment will be capped at 10% per site (200 patients) and 40% per country (800 patients). This cap includes collection of patient data both prospectively and retrospectively.

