### **Informed consent**

Patients who fulfil the criteria above will be contacted either at clinic during their next routine follow up cardiology appointment, or by phone and / or mail. The approved informed consent form will then be discussed in detail with the patient and if they agree to take part, the patient will personally sign and date the consent form.

If local regulations permit, sites may also ask their IEC for an informed consent waiver.

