## **10 STATISTICAL METHODS AND ANALYSES**

### **10.1 Analysis Population**

The population for analysis includes all enrolled patients who are documented as having received vernakalant IV.

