### **12.1 Patient Information and Informed Consent/Accent**

It is expected that a prerequisite for a patient's participation in the study is informed consent from the patient or a legal representative; however the possibility of conducting this study with a waiver of consent will be explored in each country.

The physician will obtain written informed consent as needed from each patient or a legal representative if incapacitated prior to enrolment and data collection. The physician, or delegated personnel, is required to provide patient or legal representative with the informed consent in their local language. The informed consent document contains adequate information on risks of study participation, in this case, limited to communication of personal identifiers and health information. This informed consent document will be approved by the appropriate EC as will any revisions to the document. Each patient or legal representative will be provided a copy of the informed consent document and the original will be maintained at the site. Confirmation of signed informed consent documents obtained as required will be one of the primary activities performed by the CRA during onsite monitoring as defined in the monitoring plan.

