Note: Total n for each variable includes non-missing observations. Percentages, where applicable, are calculated with non-missing observations in denominator unless otherwise noted.

¹Analysis population set is defined as all treatment episodes among enrolled patients who meet the eligibility criteria and sign the informed consent form and are administered vernakalant IV.

²Number of patients with multiple enrolments in SPECTRUM.

³Effectiveness analysis population set is defined as all treatment episodes among patients from the analysis population set except for those treatment episodes in which patients receive another therapy for cardioversion within 90 minutes of start of the first vernakalant IV administration (i.e. electrical or pharmacologic cardioversion).

⁴Includes patients with single or multiple enrolments.

⁵Patients who discontinued the study for any reason or who did not have a complete end of study form as of the time of data extraction for interim reports.

Table 3 Overview of Enrolled Patients in the Analysis Set by Enrolment Period and Country

| Country | Analysis Set (N = xxx) | Prospective Patients (N = xxx) | Retrospective Patients (N = xxx) |
|-----------|---------------------------|-----------------------------------|-------------------------------------|
| Country 1 | xx (xx.x%) | xx (xx.x%) | xx (xx.x%) |
| | | | |
| Country 2 | xx (xx.x%) | xx (xx.x%) | xx (xx.x%) |
| | | | |
| Country 3 | xx (xx.x%) | xx (xx.x%) | xx (xx.x%) |
| | | | |
| Etc. | | | |

Note: Total n for each variable includes non-missing observations. Percentages, where applicable, are calculated with non-missing observations in denominator unless otherwise noted.

Table 4.1 Patient Demographics, All Enrolled Patients

| Characteristic | Analysis Set (N = xxx) | Prospective Patients (N = xxx) | Retrospective Patients (N = xxx) |
|---|---------------------------|-----------------------------------|-------------------------------------|
| Age (years) | | | |
| n | XXX | XXX | XXX |
| Mean (SD) | xx.x (xx.xx) | xx.x (xx.xx) | xx.x (xx.xx) |
| Median | xx.x | xx.x | xx.x |
| Q1, Q3 | xx.x, xx.x | xx.x, xx.x | xx.x, xx.x |
| Min, Max | xx.x, xx.x | xx.x, xx.x | xx.x, xx.x |
| Missing | xx | xx | xx |
| Gender | | | |
| n | XXX | XXX | XXX |
| Male | xx (xx.x%) | xx (xx.x%) | xx (xx.x%) |
| Female | xx (xx.x%) | xx (xx.x%) | xx (xx.x%) |
| Missing | xx | xx | xx |
| Race¹ | | | |
| n | XXX | XXX | XXX |
| White | xx (xx.x%) | xx (xx.x%) | xx (xx.x%) |

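### SAP 3.4 dates age and the gap between treatment episodes from consent, which for retrospective patients can fall years after treatment; the analysis-set wording and incidence footnotes also need aligning

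*SAP*

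**What the plan says.** **Dates.** SAP 3.4 computes age as consent date minus birth date, with self-reported age used only when the birth date is missing. SAP 5.1.3 repeats that age is taken at consent. SAP 3.4 also computes the time between enrolments as one consent date minus the previous one. Listings 7 and 8 print that quantity in a column headed as days between treatment episodes, with a footnote saying that it rests on consent dates.

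**Analysis set.** SAP 4.2 states: "All enrolled patients who meet the eligibility criteria, sign the informed consent form, and are administered vernakalant IV will be included". It adds: "All the summaries will be presented on the overall analysis population set unless otherwise stated". SAP 5.1.1 repeats the condition, and Table 2 footnote 1 defines the set as episodes among "enrolled patients who meet the eligibility criteria and sign the informed consent form and are administered vernakalant IV". Protocol 10.1 has no consent condition: "The population for analysis includes all enrolled patients who are documented as having received vernakalant IV".

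**Consent routes.** For retrospective patients, Protocol 7.2 provides that "the patient will personally sign and date the consent form", but also that "If local regulations permit, sites may also ask their IEC for an informed consent waiver". Its list of conditions reads "Provide their informed consent or the site obtains a waiver from their IEC". The schedule in Protocol 7.1.2 allows proxy consent or a waiver, and Protocol 12.1 says: "however the possibility of conducting this study with a waiver of consent will be explored in each country". The SAP does not mention waivers.

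**Denominators.** For health outcomes of interest (HOIs), SAP 5.4 and Table 8 footnote 1 divide by patients enrolled and treated; Table 8 footnote 2 divides by patients enrolled. For SAEs, SAP 5.7 divides by the analysis population set; the Table 16 footnotes divide by patients enrolled.

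**The concern.** Consent is a workable time origin when it is given around the time of treatment, as for prospective patients. Section 7.2 of the protocol added patients who are contacted at a later clinic visit, by telephone or by mail, possibly years after the infusion. The consent date then says when the site reached the patient, not when the patient was treated. The age error falls almost entirely in the retrospective column of tables that set prospective and retrospective patients side by side. A consent-to-consent gap cannot serve a reader who wants to know how soon after an earlier exposure an event occurred. For a patient entered by waiver there is no consent date: the gap is undefined, and so is age when the birth date is known. SAP 4.4 rules out imputation.

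The other two points concern who is counted. Read literally, a treated waiver patient leaves every default summary and the SAE incidence in SAP 5.7, yet stays in the SAP 5.4 denominator. And SAP 5.1.1 shows that enrolled is not the same as treated, because some enrolled patients convert to sinus rhythm before dosing.

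**Working it through.** **The plan's own figure.** SAP Table A gives Clopper-Pearson limits: lower = Beta quantile(0.025; x, n − x + 1), upper = Beta quantile(0.975; x + 1, n − x), with x = p × n. For p = 0.003 and n = 1,500 this gives 0.00090 to 0.00729 and a margin of 0.00429, against the stated 0.001, 0.007 and 0.004. All 44 pairs of limits in the table reproduce. The precision statement is not in dispute.

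**Age.** Inputs: treatment since April 2013 (Protocol 7.2); recruitment target Q4 2017, with 435 retrospective patients planned (Protocol Appendix I); total 2,000.
- Largest lag: 1 April 2013 to 31 December 2017 = 1,735 days = 4.75 years; from the end of April 2013 it is 4.67. Range 0 to about 4.7 years.
- Typical lag, assuming treatment spread evenly from 1 April 2013 to 3 August 2016 (protocol date) and consent spread evenly from then to 31 December 2017: midpoints 2 December 2014 and 17 April 2017, a difference of 2.37 years.
- Overall mean age: 2.37 × 435/2,000 = 0.52 years; at most 4.7 × 435/2,000 = 1.02 years.
- MDRD eGFR varies as age to the power −0.203. With a 4.7-year error: (74.7/70)^−0.203 − 1 = −1.3% at a true age of 70, and (54.7/50)^−0.203 − 1 = −1.8% at 50.

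**Episode gap** (constructed examples).
- Two retrospective episodes, 1 May 2013 and 1 May 2016, consented at one visit: true gap 365 + 365 + 366 = 1,096 days; listed gap 0.
- A retrospective episode on 1 May 2014 consented on 15 January 2017, then a prospective episode treated and consented on 15 March 2017: true gap 1,049 days; listed gap 59.

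**Analysis set.** Protocol 10.1 requires enrolled plus documented as treated. The SAP adds a signed form. Eligibility and consent are ordinarily conditions of enrolment, so for most patients the two sets coincide. They part for a patient entered by waiver, who is enrolled and treated but has signed nothing. The documents give no count of waivers, so no size can be computed.

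**Denominator.** Take 4 events in 2,000 treated patients, close to the highest trial rate in SAP 4.1 (0.22% × 2,000 = 4.4), and assume 0, 20 or 100 further patients enrolled but never dosed:
- 4/2,000 = 0.200% (95% CI 0.055 to 0.511)
- 4/2,020 = 0.198% (0.054 to 0.506)
- 4/2,100 = 0.190% (0.052 to 0.487)

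SAP 5.11 reports percentages to one decimal, so all three print as 0.2%. The Table 8 shell shows limits to two decimals, where the upper limit moves from 0.51 to 0.49 only in the last case.

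**The case against.** The strongest reply is that none of this touches a primary estimate. The age variable is openly labelled as age at enrolment, the basis of the gap is disclosed in a footnote, and the gap appears only in descriptive listings. That is right about consequence. It does not rescue the listings, whose column heading promises time between treatments and whose rule does not deliver it.

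On waivers, the consent phrase may be boilerplate. SAP 5.1.1 ends its disposition list with exclusions for spontaneous conversion and withdrawn consent only, with no line for a treated patient without a signed form. The protocol says that a waiver may be sought or explored; nothing shows that one was granted. This stands: exclusion was probably not intended, and the number affected may be zero.

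A reader might go further and infer that the signed-form rule removes fatal cases, since a retrospective patient who has died cannot sign personally. The documents do not support that as a finding. Protocol 7.2 applies the same inclusion criteria to both groups, and those mention legal guardians. If no waiver exists, deceased retrospective patients are simply never enrolled, which is a selection limit of the protocol that SAP wording cannot cure.

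A reader might also infer that the HOI and SAE tables use different denominators. Table 8 footnote 2 and the Table 16 footnotes use the same one. The contradiction is between footnotes and text, and between the two footnotes of Table 8. The overall tables are titled for the analysis set, so enrolled may be shorthand.

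**Conclusion.** The dating rule is wrong for retrospective patients. Age is overstated by 0 to about 4.7 years in that column: about 2.4 years on average and 0.5 years across all patients under the even-spread assumption and the planned 435 of 2,000, with eGFR lowered by no more than about 2% at the ages examined. Gaps in Listings 7 and 8 can be wrong by years for an individual. For any waiver patient the gap is undefined, and so is age when the birth date is known.

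The signed-form condition conflicts with Protocol 10.1 and with the waiver routes, but its effect is unknown and may be nil. The footnote denominators contradict the SAP text. With up to 100 undosed patients (assumed), the point estimate does not change as printed and the upper limit moves by at most 0.02 percentage points. These are defects of definition worth correcting; the documents do not show that any HOI, SAE or effectiveness result would change materially.

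**What to change.** - **SAP 3.4, 5.1.3, Table 4.1, Listings 7 and 8:** compute age and the time between treatment episodes from the start date of the first infusion. Table 7.1 footnote 17 warns that this date may be missing for retrospective patients. In that case use the admission date, which Protocol 7.1.1 collects and 7.2.1 does not exempt, and flag the value. State this as an explicit exception in SAP 4.4, because it is otherwise at odds with the no-imputation rule.
- **SAP 4.2, 5.1.1, Table 2 footnote 1:** define the analysis set as in Protocol 10.1, namely patients enrolled by signed consent, legal-representative consent or approved waiver and documented as having received vernakalant IV.
- **SAP 5.4, 5.7 and the Table 8 and Table 16 footnotes:** use that one set as the denominator. The Table 17 footnote also divides by patients enrolled and should follow.

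The cost is SAP wording, two derivation rules and a flagged fallback date for some retrospective patients. No protocol or enrolment change is needed. No separate waiver field is needed either, because the set is everyone enrolled and treated.

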4.3 Subgroup Analysis

The tables relating to patient selection (i.e., demographics, presenting conditions, and medical history) and vernakalant dosing and administration will be repeated for each country. Country-specific tables will include:

- **Table 1.2** Use of Pre-Infusion Checklist Prior to Vernakalant IV
- **Table 1.3** Receipt of Healthcare Provider (HCP) Educational Card, by Site
- **Table 4.1** Patient Demographics
- **Table 5** Other Baseline Presenting Conditions and Medical History
- **Table 9.1** Vernakalant IV Administration and Dosing (Overall)
- **Table 9.2** Vernakalant IV Administration and Dosing (Prospective Patients)
- **Table 9.3** Vernakalant IV Administration and Dosing (Retrospective Patients)
- **Table 10** Patient Age and Therapeutic Indication for Use in Accordance with the Vernakalant IV Summary of Product Characteristics
- **Table 11** Contraindications for Use in Accordance with the Vernakalant IV Summary of Product Characteristics

Rates of HOIs will not be reported by country or other specified subgroups as individual events are expected to be rare, and stratification of event rates will yield statistically unstable results.

Secondary analysis of rates of HOIs may be conducted for subgroups of patients with certain medical characteristics if the sample size is sufficient to allow for reasonably precise point estimates of HOI incidence (in general, 500 patients or more). Regardless, a description of each patient with an SAE or HOI will be given in narrative form.

A pre-specified secondary analysis of the effectiveness of vernakalant will be restricted to a subgroup of patients who receive vernakalant IV in accordance with the Summary of Product Characteristics (SmPC). Specifically, the following patients will be **excluded** from the pre-specified subgroup analysis:

- Patients not administered vernakalant IV in accordance to SmPC in terms of adult indication (age < 18 years of age), therapeutic indication (indication other than conversion of atrial fibrillation), duration of atrial fibrillation (atrial fibrillation > 7 days for non-surgery patients and > 3 days for post-cardiac surgery patients).
- Patients with at least one of the following contraindications: baseline systolic blood pressure < 100 mmHg, MI/ACS past 30 days, severe aortic stenosis, severe bradycardia in absence of pacemaker, prolonged QT at baseline (uncorrected > 440 msec) in absence of pacemaker, sinus node dysfunction in absence of pacemaker, 2nd or 3rd degree heart

block in absence of pacemaker, heart failure NYHA functional class III or IV, use of class I or class III intravenous anti-arrhythmics within 4 hours before, or within 4 hours after, the start of first vernakalant infusion).

In addition, the effectiveness of vernakalant will be evaluated by the indication of use for which vernakalant IV was prescribed (i.e., conversion of atrial fibrillation for non-surgery patient and conversion of atrial fibrillation for post-cardiac surgery patients).

